6.2 ANALYSIS PLAN

Data will initially undergo extensive logic and consistency checks and any potential errors will be resolved through discussion with cohort/clinic data managers.

Proportions with SARS-CoV-2 antibody at baseline and follow-up and the number/incidence of changes in antibody status between baseline and subsequent test will be estimated overall and by key patient characteristics, region, history of symptomatic COVID-19, contact with COVID-19 cases, receipt of COVID-19 vaccine. Factors associated with the presence of SARS-CoV-2 antibody, changes in

antibody status and any subsequent COVID-19 diagnosis (if numbers allow), will be explored using univariable and multivariable logistic and Poisson regression. Exposures of interest include age, sex, ART class and regimen (e.g. protease inhibitor- or tenofovir-based versus other), CD4 count, viral load, ethnicity, BMI-for-age z-score, co-infections (e.g. tuberculosis), co-morbidities, receipt of/duration since COVID-19 vaccine and household size.

The association between HIV status and SARS-CoV-2 seropositivity, changes in antibody status and subsequent COVID-19 diagnosis will be assessed in the South African cohort (which includes HIV-uninfected children as well as CLWHIV) using similar methods. Directed acyclic graphs may be used to determine which covariates to include in the models and to aid interpretation of the results.

If there is substantial variation in the type of antibody test used (anti-S versus anti-N), analyses will be stratified by type of test. For participants with positive results at both baseline and follow-up and if data allow, quantitative antibody results will be explored to qualitatively describe the possible contribution of re-exposure boosting antibody responses (versus persistence of an existing response).

In sensitivity analyses, we will investigate the implications of misclassification of results due to imperfect sensitivity / specificity of the serological tests used.

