Scientific knowledge about the COVID-19 pandemic and the virus that is causing it (SARS-CoV-2) is developing rapidly, and we have a clearer idea of the population groups who are at higher risk of becoming infected, having serious illness, and dying. However, less is known about COVID-19 in children, adolescents and young adults living with HIV. It is not yet known whether, or how, HIV affects people's risk of being infected with the virus or becoming ill. This study aims to find out whether children and adolescents living with HIV have had the COVID-19 virus, even if they did not have symptoms and did not realise it at the time.

When a person is infected with a virus, their immune system fights the infection. As a result, they produce proteins called antibodies, and it may take a few weeks for enough antibodies to be made to be detected by a blood test. These antibodies may help protect the person from getting the same infection again. In this study, we want to find out how many children and adolescents living with HIV across Europe and South Africa have antibodies to the COVID-19 virus. We want to see if the proportion with antibodies is different in younger children compared to older adolescents and young adults, and whether it varies between different countries.

Some countries are rolling out vaccines against COVID-19 and have prioritised people living with HIV. We do not know if the immune response to vaccines in people living with HIV is similar to those without HIV, how long the antibodies last for and if it varies by age or any other characteristic.

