1.2 OBJECTIVES

Primary objective:

- To estimate prevalence of SARS-CoV-2 antibodies in the paediatric and adolescent HIV population and how this changes over time, overall and by key age groups and regions

Secondary objectives:

- To assess factors associated with presence of SARS-CoV-2 antibodies (including demographic factors, antiretroviral treatment, HIV-associated factors or co-morbidities and exposure to household members with COVID-19, receipt of COVID-19 vaccine)
- To estimate the incidence of changes in antibody status to SARS-CoV-2 and associated factors

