3 STUDY PROCEDURES

3.1 STUDY DESIGN

This is a serial point prevalence survey of representative samples of children and adolescents attending routine HIV care in the participating clinics and cohorts, with repeat antibody testing at baseline (study entry) and approximately 6 months after study entry (Table 1), and in some clinics further long-term follow-up through linkage to data collected in an ongoing longitudinal cohort study. In South Africa approximately 50-100 HIV-uninfected adolescents enrolled in the ongoing CTAAC cohort will be invited to participate in this study as a comparator group.

Eligible participants who are interested in joining the study will be asked for their consent to participate if aged ≥ 16 years or as per local legal requirements. For participants aged <16 years, consent of their parent/carer will be sought as per legal requirements. Assent will be sought from children and adolescents aged 10 years and older, depending on local ethics requirements. Potential participants and their parents / carers should be allowed at least 5-10 minutes to consider whether or not to take part; where possible, it may be helpful to give patients copies of the participant information sheet while they wait for their appointment.

Data collection will be conducted at HIV clinics during routine visits in clinical care (in the European cohorts) or planned study visits (in CTAAC, for both CLWHIV and HIV-uninfected adolescents), and no additional study visits will be required.

At entry to the study the participant will give a venous blood sample for a SARS-CoV-2 antibody test (the exact test used will depend on local clinical practice). An additional serum sample will be taken at the same time as a routine blood draw and leftover sample will be used if possible. At the next scheduled routine HIV clinic/study visit approximately 6 (no less than 3 and up to 13) months later, a repeat venous blood sample will be collected for a second antibody test. At each visit, participants (or their parents/carers) will be given a COVID-19 questionnaire, asking short questions about any COVID-19 diagnoses in themselves or among household members and other possible exposures to the virus. All study procedures will be carried out following local COVID-19 guidelines.

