If participants have previously (after 1 March 2020 and at least four months before the date of the first sample collected as part of this study) had a blood sample tested for SARS-CoV-2 antibody as part of their routine HIV care or another research study (for which the result is available in their medical records), that test will be considered as the first test for this study. These participants would therefore provide an additional blood sample at only one study visit. Clinical data corresponding to the time of the first sample collection will be extracted.

If participants have previously (after 1 March 2020 and at least four months before the date of the first sample collected as part of this study) had blood taken for other reasons that is still stored, this may also be tested for SARS-CoV-2 antibodies. In these cases, this would be considered the first test for this study and these participants would provide an additional blood sample at only one study visit. Clinical data corresponding to the time of the first sample collection will be extracted.

Participants who are followed in cohorts which are part of the EPPICC network will continue to be followed up through the ongoing EPPICC Paediatric Study.

Table 1: Study participant timeline

	Baseline	2nd visit at 6 months*
Eligibility screen	X	
Informed consent	X	
Blood sample for SARS-CoV-2 antibody	X	X
COVID-19 patient questionnaire	X	X
Clinical data collection	X	X

* Participants who have results available from a previous blood test for SARS-CoV-2 antibody in the previous 4 months (as part of routine care or research) do not require a second test.

Participants will be given the result of their SARS-CoV-2 antibody tests with guidance on how to interpret the results, unless this conflicts with the clinic or study's usual practice.

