3.2 ENROLMENT AND FOLLOW-UP

We aim to start enrolment from November 2020 (pending ethics approval) and enrol participants for approximately twelve months or until the sample size is met. The enrolment period may be extended in the event of disruptions to clinic services due to COVID-19. Where feasible, all children and adolescents meeting the inclusion criteria and attending the participating clinics during this period will be invited to take part; where this is not possible, a convenience sample of children and adolescents (e.g. those attending clinic on a specified day of the week) should be invited. The invitation to participate should be independent of the patient's probability of having been exposed to COVID-19.

Participants will be considered lost to follow-up for the purposes of this study if they have not provided the second blood sample by 13 months after the enrolment date.

Participants enrolled in the EPPICC Paediatric Study or CTAAC will continue to be followed up as part of the ongoing study.

Logs will be kept of the number of children and adolescents declining the invitation to participate, with reasons for refusal where available.

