6 STATISTICAL CONSIDERATIONS

6.1 SAMPLE SIZE

The total sample size is 1150, with provisional numbers eligible by cohort summarised in Table 3. Allowing for 70% participation, the target sample size can be met within the participating cohorts. At some sites within EPPICC, participants will receive SARS-CoV-2 serological tests as part of routine care or within an ongoing research study, and a repeat test will be offered as part of this study approximately six months after (no less than 3 and up to 13 months) the first sample; however both sets of results will be collected in this study. At other sites and in South Africa, both tests will be part of this study.

In addition, some sites may be able to test stored samples taken for other purposes and not previously tested for SARS-CoV-2 antibodies. In these cases, this would be considered the first test and the participant would have one additional test as part of this study approximately six months (no less than 3 and up to 13 months) after the first sample date.

Table 3: Provisional numbers of eligible participants (aged <25 years) per cohort

Cohort	Number of eligible participants	
	CLWHIV	HIV-uninfected adolescents
Belgium	74	0
Greece	22	0
CoRISPES (Spain)	250	0
CoRISPE-Cat (Spain)	50	0
Sweden	85	0
Ukraine	170	0
United Kingdom	442	0
EPPICC Total	1093	0
South Africa	400	50-100
Total	1493	50-100

Assuming an overall anti-SARS-CoV-2 prevalence of 10%, similar to that reported for children aged 10-19 years in Geneva, Switzerland [3], the sample size would result in a 95% confidence interval of +/- 2% in Europe and +/-3% in South Africa.

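### Prevalence by region and its change over time are to be estimated by visit label, not by calendar date of sample, although the two visits overlap in calendar time and some cohorts can have earlier first tests

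*Combined protocol and SAP*

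**What the plan says.** Section 1.2 sets the primary objective as prevalence "and how this changes over time, overall and by key age groups and regions". The lay summary adds the question of the age pattern "and whether it varies between different countries".

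Section 6.2 plans to estimate "Proportions with SARS-CoV-2 antibody at baseline and follow-up and the number/incidence of changes in antibody status", overall and by patient characteristics, region, COVID-19 history, contact and vaccination. Neither these breakdowns nor the listed regression exposures include the calendar date or period of the sample. The only time variable is time since vaccination. The one sensitivity analysis concerns test misclassification.

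Four other provisions decide when samples are taken:

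- Section 3.2: enrolment is to start in November 2020 and to "enrol participants for approximately twelve months or until the sample size is met", with extension possible.
- Section 3.1: "approximately 6 (no less than 3 and up to 13) months later, a repeat venous blood sample will be collected".
- Section 3.1: an existing antibody result, or a stored sample, may serve as the first test if dated "after 1 March 2020 and at least four months before the date of the first sample collected as part of this study". For stored samples, "this would be considered the first test for this study and these participants would provide an additional blood sample at only one study visit".
- Section 6.1: "At some sites within EPPICC, participants will receive SARS-CoV-2 serological tests as part of routine care or within an ongoing research study". At the remaining sites and in South Africa both tests belong to the study. The next paragraph says that some sites may test stored samples, and does not name them.

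Table 2 in section 4.1 lists the date of test and the site identifier among the data collected.

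**The concern.** SARS-CoV-2 seroprevalence depends strongly on calendar date. The protocol's own background section attaches a date or sampling period to each prevalence figure that it cites. A visit label is not a date here. One participant's follow-up sample can be drawn months before another's baseline sample, and the mix of dates behind each label can differ between cohorts because earlier first tests are available only in some of them.

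Two results in the primary objective are affected. First, a cohort with earlier first tests can show lower prevalence than another on the same epidemic curve. Its follow-up samples are earlier too, so that visit is affected in the same way. Second, the change from baseline to follow-up averages over many different intervals of the epidemic and cannot be read as a change between two known times.

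**Working it through.** **Plan's own figure.** The 95% half-width at prevalence 0.10 is 1.96 × √(0.10 × 0.90 / n). This gives 2.3 points for n = 650 (Europe), 2.6 for n = 500 and 2.9 for n = 400 (South Africa, all or those living with HIV). These round to the ±2% and ±3% in section 6.1. The precision statement is not in question, but it has no date attached.

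**Calendar windows** (months from 1 March 2020; November 2020 = 8, November 2021 = 20).

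- First samples: 0 to 20 if earlier samples count, 8 to 20 if both tests are in the study.
- Second samples start at month 8 for a participant who has an earlier first test and enrols at once. With both tests in the study they start at 8 + 3 = 11 (minimum gap) or 8 + 6 = 14 (nominal gap).
- Overlap of the two sets: 20 − 8 = 12 months at the outer limit. With both tests in the study it is 20 − 11 = 9 or 20 − 14 = 6 months, which is ordinary rolling enrolment.

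**Regional shift (illustration).** The documents give neither the epidemic curve nor the share f of earlier first tests, so both are assumed. Study entry is uniform over months 8 to 20 (mean 14), the gap is 6 months, and an earlier first test falls 6 months before entry. Prevalence rises linearly from zero by k points a month and is identical in both cohorts. One cohort has share f of earlier first tests and the other none, which is the extreme contrast.

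Mean baseline is 14k without earlier tests and (14 − 6f)k with them, so the difference is 6kf. Follow-up differs by the same amount. The last column is the half-width 1.96 × √(p₁(1−p₁)/650 + p₂(1−p₂)/400), where p₁ and p₂ are the two baseline prevalences.

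| Curve | k | Baseline without earlier tests | Shift at f = 10/25/50% | Half-width, 650 v 400 |
|---|---|---|---|---|
| Mean baseline 10% (section 6.1 value) | 10/14 = 0.714 | 10% | 0.4 / 1.1 / 2.1 | 3.7 / 3.7 / 3.6 |
| 30% in November 2021 | 30/20 = 1.5 | 21% | 0.9 / 2.3 / 4.5 | 5.0 / 5.0 / 4.9 |
| 50% in November 2021 | 50/20 = 2.5 | 35% | 1.5 / 3.8 / 7.5 | 5.9 / 5.9 / 5.8 |

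Only the last shift (7.5 against 5.8) exceeds the sampling half-width.

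**Pooled change (illustration).** On a linear curve with equal gaps every pair rises by 6k, so earlier tests change nothing. For an S-shaped wave, 30% / (1 + exp(−(t − m)/1.5)), with share f taken over the pooled sample, the mean change in points is:

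| Wave centre m | f = 0 | f = 25% | f = 50% |
|---|---|---|---|
| 8 (November 2020) | 2.5 | 5.0 | 7.5 |
| 10 (January 2021) | 5.6 | 7.7 | 9.8 |
| 14 (May 2021) | 12.4 | 12.4 | 12.4 |
| 16 (July 2021) | 13.9 | 12.8 | 11.6 |
| 18 (September 2021) | 13.9 | 11.8 | 9.8 |

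The shift runs from about +4.9 through zero to −4.1 points. For scale, a 9-point paired change in 650 people without seroreversion has half-width 1.96 × √(0.09 × 0.91 / 650) = 2.2 points. At the May 2021 centre the pooled change does not move, but baseline in the two-cohort contrast still differs by 3.1 points (25%) or 6.2 points (50%).

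**The case against.** The stated aim is descriptive. The exposure list in section 6.2 is open-ended, and directed acyclic graphs may guide covariate choice in the HIV-status analysis. Vaccination and time since vaccination are included, which covers part of any calendar trend. Much of the overlap is what rolling enrolment always produces. At the protocol's own 10% prevalence the shift is small against sampling error. All of this stands and limits the point. None of it commits the plan to using sample date, and covariate choice does not reach the prevalence proportions, which are not model outputs.

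A reader might also infer stronger things that the documents do not support:

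- *That the regional comparison will be falsely significant at some computed rate.* Section 6.2 estimates prevalence by region. It specifies no regional hypothesis test, and region is not among the listed regression exposures. The shift in points is the relevant measure.
- *That earlier first tests are confined to Europe.* This holds for routine and research tests. The stored-sample sentence in section 6.1 is not limited to EPPICC, and the documents do not settle whether South Africa may use it.
- *That the change over time is wrong.* Each participant's two samples stay in time order, and under some curves the pooled change does not shift at all.
- *That the dates are missing.* They are collected; no analysis is said to use them.

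**Conclusion.** The point holds as a gap in the analysis plan. The primary objective concerns time and region, while the stated estimator is indexed by visit label and so mixes calendar time with region. The size is unknown, because it depends on the share of earlier first tests and on the epidemic curve, and the documents give neither. On the assumed linear curves the regional baseline shift runs from 0.4 to 7.5 points, using the extreme contrast of some earlier tests against none. It exceeds the sampling half-width only at a 50% share on the steepest curve. The pooled change shifts by zero to several points, in either direction. These are differences between mixes of calendar periods, not bias against a known true value.

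The HIV-status comparison within South Africa is little affected if both groups there are tested within the study, as section 6.1 indicates. The mention of incidence and Poisson regression suggests person-time, but section 6.2 does not say so, and person-time would not place the prevalence estimates in calendar time. This is a cheap improvement, not a flaw that invalidates the study.

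**What to change.** In section 6.2:

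1. Report prevalence by calendar period of sample within region, using samples from both visits with standard errors clustered by participant. Compare regions only in periods where both have samples.
2. Include calendar period and region in the seropositivity models, with a region-by-period term where numbers allow. A single region effect assumes the same contrast in every period, which fails if regional waves differ.
3. State that the incidence of changes in antibody status uses person-time between samples.

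Keep the baseline and follow-up tables as description. A table of sample dates by visit and region would show how far the labels overlap.

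**Cost.** No new data are needed, only plan wording and modest analysis work. Intervals per period are wider. With both tests in the study, even enrolment over four quarters, 6-month gaps and no losses, Europe has 650/4 ≈ 163 samples in a quarter with one visit's samples and 325 where the visits overlap. At 10% prevalence the half-width is ±4.6 to ±3.3 points, against ±2.3 for all 650. South Africa (400 living with HIV) has 100 to 200 per quarter, or ±5.9 to ±4.2, against ±2.9. Small cohorts, such as Greece with 22 eligible, cannot support country-level terms.

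The adjusted region contrast loses little. In a simulation of 650 v 400 (30% curve, 25% share, both visits, clustered standard errors), the standard error of the log odds ratio was about 0.139 without quarter terms and 0.143 with them.

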3.4 LABORATORY TESTING

Where sites are conducting serological testing as part of standard care, venous blood samples taken at each site will be transported to the laboratory(ies) routinely carrying out antibody testing for that site. Samples will be analysed with the tests used by each site in routine practice according to manufacturers' instructions or, if in-house tests are used, local SOPs/protocols.

At sites not offering routine serological testing, arrangements should be made with local laboratories for testing. There is strong preference for tests for IgG against the viral spike protein as data suggests this has the longest half-life; however, it is recognised that there may be local considerations influencing the range of tests available across settings and results from other tests will be considered.

Where possible, antibody test results will be reported both categorically (e.g. positive, negative, equivocal) and quantitatively (e.g. antibody titre). Results will be transferred securely as described in Section 4.2.

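### The planned models for change in antibody status name neither the first antibody level nor time since infection, so an exposure linked to earlier infection can look like a cause of antibody loss

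*Combined protocol and SAP*

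**What the plan says.** Section 1.2 lists as a secondary objective "To estimate the incidence of changes in antibody status to SARS-CoV-2 and associated factors". Section 6.2 carries this out in two steps. First, "the number/incidence of changes in antibody status between baseline and subsequent test will be estimated overall and by key patient characteristics". Second, the factors associated with such changes "will be explored using univariable and multivariable logistic and Poisson regression". Loss and gain of antibody are not separated.

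The exposure list is worded as open: "Exposures of interest include age, sex, ART class and regimen" and so on, ending with "receipt of/duration since COVID-19 vaccine and household size". The only timing variable in it is time since vaccination. In the paragraph on the South African comparison by HIV status, 6.2 adds: "Directed acyclic graphs may be used to determine which covariates to include in the models". That is an option, and it fixes no covariate.

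Section 3.4 says that, where possible, "antibody test results will be reported both categorically (e.g. positive, negative, equivocal) and quantitatively (e.g. antibody titre"). Table 2 in 4.1 also collects the result in both forms. The one use of quantitative results stated in 6.2 is a qualitative description of participants positive at both tests, which leaves out everyone who lost antibody.

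**The concern.** Whether a first-test positive becomes negative depends on how far above the cut-off that person started and how fast the level falls. The starting distance depends in turn on the time from infection to the first test. If that time differs between the groups compared, the group infected earlier crosses the cut-off more often, with no difference in decay.

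The design lets this time vary. The first sample may be a past or stored one taken after 1 March 2020 (3.1), enrolment lasts about twelve months (3.2), and Section 1 suggests that the pandemic arrived later in the African region. The lay summary expects some infections to have gone unnoticed, so a diagnosis date will often be missing. The first level is then the practical marker of where a participant started.

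What is at stake is interpretation of a secondary objective. An association that reflects infection date could be read as a difference in how well antibody is maintained.

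**Working it through.** **The plan's own figure.** 6.1 assumes 10% prevalence. The half-width is 1.96 × √(0.1 × 0.9/n): 2.31% for n = 650 (Europe), and 2.63% for n = 500 or 2.94% for n = 400 (South Africa with and without 100 uninfected participants). These match the stated 2% and 3% after rounding. The same 10% gives the number at risk of loss: 65 + 50 = 115 first-test positives.

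**Inputs.** From the documents: about 6 months between tests (3.1). Assumed, because the documents give no decay rate or level distribution:
- first level X in doublings above the cut-off, Normal with mean μ = 3 or 4 and SD 1.5, kept if X > 0;
- half-life h = 3 to 6 months, the same for everyone;
- second level Y = X − 6/h + e, with e Normal, SD 0.5; loss if Y < 0;
- the other group infected d = 3 or 6 months earlier, so its mean is μ − d/h.

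**Formula.** P(loss) = ∫₀^∞ φ((x − m)/1.5)/1.5 × Φ((6/h − x)/0.5) dx ÷ Φ(m/1.5), with m = μ or μ − d/h.

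| h (months) | μ | Later-infected | 3 months earlier | OR | 6 months earlier | OR |
|---|---|---|---|---|---|---|
| 3 | 4 | 9.9% | 24.6% | 2.96 | 45.0% | 7.40 |
| 3 | 3 | 24.6% | 45.0% | 2.50 | 64.7% | 5.62 |
| 6 | 4 | 2.5% | 4.8% | 1.94 | 8.2% | 3.47 |
| 6 | 3 | 8.2% | 13.0% | 1.67 | 19.0% | 2.62 |

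**Adjusting for the first level.** With X measured without error, a logistic model including X returns an odds ratio of about 1.0; the model guarantees this. With assay error of 0.3 to 0.5 doublings at the first test, the adjusted odds ratio is about 1.0 to 1.3 for 3 months and 1.1 to 1.7 for 6 months.

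**A second model.** Let the peak level be Normal(μ, s) and the first test fall t months after infection. Then P(loss) = 1 − Φ((μ − (t + 6)/h)/s) ÷ Φ((μ − t/h)/s). For μ = 3, s = 1.5, h = 4:
- t = 2: 1 − Φ(0.667)/Φ(1.667) = 21.5%;
- t = 8: 1 − Φ(−0.333)/Φ(0.667) = 50.6%; risk ratio 2.35.

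Over 18 combinations (μ 2, 3, 4; s 1.5, 2; h 3, 4, 6) the risk ratio for 8 versus 2 months was 1.48 to 3.72. In the case shown, stratifying by first level brought it to 1.00 without assay error and 1.05 with error of 0.3 doublings.

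**Where the effect fails.** If log levels above the cut-off are exponentially distributed, loss does not depend on t and the effect vanishes. With two-phase decay (fast half-life 1 to 3 months for 4 months, then 6 to 12; μ = 4, s = 2) the risk ratio ranged from 0.45 to 1.53.

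**How the level is scaled.** Suppose each group uses its own kit and the level enters as a within-kit z-score. In the first model with d = 3, the odds ratio becomes about 22 to 23 (h = 3, μ = 4) and about 3.6 (h = 6, μ = 3), worse than no adjustment. The z-score removes the between-group difference in distance from the cut-off, which is the confounder.

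**Precision.** Split 115 positives evenly (57.5 each). With 9.9% v 24.6% there are about 20 losses; SE(log OR) = √(1/5.7 + 1/51.8 + 1/14.1 + 1/43.4) = 0.54, so the odds ratio of 2.97 has a 95% CI of about 1.04 to 8.5. With 8.2% v 13.0% there are about 12 losses, and 1.67 has a CI of about 0.50 to 5.6.

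**The case against.** The strongest reply is that 6.2 fixes no model. The exposures are introduced by an open verb, causal diagrams may guide covariate choice, and the analysis is described as exploratory. A reader might infer that the plan shuts the first level out; the text does not support that. What stands is that nothing commits the analysis to using it, and that the plan names timing for vaccine-derived antibody without a counterpart for infection.

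Second, the direction and size are assumed. As shown above, the effect can vanish or reverse. In the two-phase case decay over the test interval is no longer the same in both groups, so that is a different situation, but the documents cannot say which applies. This objection stands.

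Third, bias needs a link between the exposure and infection date. The documents make that plausible for region or cohort. They give no infection dates by age, regimen, CD4 or household size, and for an exposure unrelated to timing the effect is absent.

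Fourth, crude loss of status is a legitimate descriptive quantity, which the objective asks for, and 6.2 does not itself interpret loss as immune durability. That is fair. The problem arises when associated factors are interpreted.

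Finally, with about 12 to 20 loss events, chance may outweigh this bias. That limits what any loss model can show, and it is also a reason to choose the few covariates in advance.

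**Conclusion.** The concern holds in a limited form. Models built only from the exposures named in 6.2 can show an association with antibody loss that reflects infection date. Under constant-rate decay, log-normal levels, half-life 3 to 6 months and a mean 3 to 4 doublings above the cut-off, the crude odds ratio is about 1.7 to 3.0 for a 3-month difference and 2.6 to 7.4 for a 6-month difference.

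A reader might infer that earlier-infected groups will always seem to lose antibody faster, that every listed exposure is affected, or that adjustment removes the bias entirely. The documents support none of these: they give no decay curve or level distribution, only exposures linked to timing are at risk, and assay error leaves some bias. The primary prevalence estimate is untouched; this is a worthwhile, inexpensive improvement to an exploratory secondary analysis.

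**What to change.** In 6.2:
- Model loss among first-test positives separately from gain among first-test negatives.
- In the loss model, add the log of the first quantitative result divided by that kit's own positivity cut-off, with kit or test type as a stratum. Do not use a within-kit z-score.
- Add time since infection where a diagnosis date exists.
- Also report the model without the level, because exposures such as CD4 may act through it.

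The cost is two or three sentences and no new data items, since the result is already sought in quantitative form. The adjusted model covers only participants with a quantitative first result. Some bias remains from assay error, and few loss events limit precision. Where a cohort uses a kit that no other cohort uses, the kit stratum also absorbs that cohort's contrast, and this should be stated when cohorts are compared.
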